The study patients will be enrolled and randomized to one of two levels of ambulatory BP control (intensive to achieve a goal 24-hour systolic BP of ≤ 130 mmHg or standard to achieve a goal 24-hour systolic BP of ≤ 145 mmHg) for a total of 36 months. Similar antihypertensive regimens will be used in both of the treatment groups with a general strategy of a renin-angiotensin blocking agent (ACE inhibitor or angiotensin blocker if ACE inhibitor not tolerated) along or in combination with a dihydropyridine calcium channel blocker and thiazide diuretics. Titration of antihypertensive therapies will be performed at monthly intervals for the first 3 to 6 months post-randomization to achieve goal systolic BP. The primary and secondary outcomes will be evaluated at baseline, and following 18 months and 36 months of therapy. Adverse events, tolerability, and health-related quality of life will be evaluated as well. Study patients will be seen on an ad hoc basis throughout the trial for any/all issues associated with blood pressure, the administered antihypertensive therapies, and adverse events.

Sample Size and Population

It is estimated that 400 potential patients will be screened with MRI of the brain to detect the presence or absence of WMH and hypertension. There will be 200 subjects with demonstrable tWMH ($> 0.5\%$ of intracranial volume) randomized into 2 groups of 100 subjects with standard (24-h systolic BP <145 mmHg) or intensive (24-h systolic BP ≤ 130 mmHg) antihypertensive therapy strategies. No stratification is planned.

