- b. We will repeat analyses 1a, 2a and 3a but with gait velocity at T₁₈, total WMH at T₁₈, and DTI indices at T₁₈ as the primary outcomes. A comparison of these analyses with analyses 1a and 1b will determine the time course of the intervention's effects. In particular, it will be important to determine if these effects occur early (T₁₈) or require a 3-year treatment period. In addition, for participants who are present at T₁₈ but not T₃₆, the data from T₁₈ will be used to estimate the effect of informative loss to follow-up. (See Missing Data)
- c. We will further examine the progression of mobility and WMH changes using a progression model using methods adapted from Diggle:³⁶

$$Y_{i0} = b_{i0} + \beta_T (X_i) + \text{cross sectional covariates} + \text{residual error}$$

$$Y_{i18} = b_{i0} + \beta_T (X_i) + \beta_L + \beta_E (X_i) + \text{cross sectional covariates} + \text{longitudinal covariates} + \text{residual error}$$

$$Y_{i36} = b_{i0} + \beta_T (X_i) + \beta_L^* + \beta_E^* (X_i) + \text{cross sectional covariates} + \text{longitudinal covariates} + \text{residual error}$$

Here, Y_{i0} , Y_{i18} , and Y_{i36} are the outcomes (mobility or imaging) at T_0 , T_{18} , and T_{36} for study participant i , and X_i is the treatment group assignment indicator for study participant i , and b_{i0} is a random intercept used to account for the fact that repeated measurements on individuals are not independent; the other β_j 's are fixed effects in this example although we will consider the possibility that treating them as random effects will add to the model fit. The model will be fit as a linear mixed model.^{37, 38} The parameters of interest are β_E , and β_E^* , the difference in the outcome progression rate (mobility or imaging) between the treatment groups at T_{18} and T_{36} . If the difference in the rate of progression is constant during follow-up, we would expect β_E^* to approximately equal $2 \times \beta_E$. This allows a more powerful and rigorous test of whether the intervention's effects are manifested quickly or over the long-term. Additional secondary analyses will use the T_{18} data to determine temporal continuity of the trends and as a partial assessment of the effect of dropout. Additional secondary analyses will use logistic regression with severity of urinary incontinence at T_{36} and T_{18} as an ordinal outcome.

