Here, Y_{i0} , Y_{i18} , and Y_{i36} are the outcomes (mobility or imaging) at T₀, T₁₈ and T₃₆ for study participant i , X_{i0} , X_{i18} , and X_{i36} the tWMH at T₀, T₁₈ and T₃₆ for study participant i , and b_{i0} is a random intercept that is used to take into account the fact that repeated measurements on individuals are not independent. The model will be fit as a linear mixed model³⁷. Again the other β_j 's are fixed effects although we will consider the possibility that treating them as random effects will add to the model fit. The parameters of interest are β_C and β_L , the cross-sectional and longitudinal effects of the imaging measures on mobility over the 36-month follow-up. As secondary analyses we will consider interactions with treatment group and nonlinear effects in time. Analyses will be repeated for the other mobility and cognitive measures, also as linear mixed models, and urinary incontinence presence/severity as binary and ordinal generalized linear mixed models.

Hypothesis 5: Total WMH at T₀ and at T₃₆ mediate the effect of treatment group, showing that

the mechanism by which reduced ABP is linked to better mobility occurs by reducing total WMH.(Paths C - A&B) Mediation models allow the evaluation of hypotheses using biological mechanisms. In this case, we believe that much of the salutary effect of reduced ABP results from reduced WMH. Assessing mediation involves estimating direct effects (Path C, above) and indirect effects (Paths A and B, above) in multistage predictor models by adding potential mediators to models describing the effect of a predictor on the outcome. To the extent by which WMH mediates the effect of BP, the effect of BP will be reduced in the model that includes WMH compared to the model not including WMH. We saw this in our observational study, as the adjusted effect of SBP in the pseudo-treatment group was reduced

from a .15 m/sec. to a .1 m/sec. difference in gait velocity when WMH was added as a model predictor.

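### The three-visit progression model is displayed with a random intercept only; if patients decline at different rates, its 36-month standard error is too small and its early-versus-late standard error too large

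*Protocol*

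**What the plan says.** In the protocol, section 8.2 (Hypotheses and Statistical Analyses), analysis c writes one equation per visit for baseline, 18 and 36 months. The only random term besides the residual is the patient intercept, which "is a random intercept used to account for the fact that repeated measurements on individuals are not independent". The remaining coefficients are "fixed effects in this example", and the sentence goes on: "although we will consider the possibility that treating them as random effects will add to the model fit". No covariance structure, selection criterion or robust standard error is named. The progression model under Hypothesis 4 has the same form; its patient term "is a random intercept that is used to take into account the fact that repeated measurements on individuals are not independent".

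The parameters that matter are `beta_E` and `beta_E*`, the treatment differences in change at 18 and 36 months. On timing, the protocol says "If the difference in the rate of progression is constant during follow-up, we would expect" the 36-month difference to be about twice the 18-month one, and then claims: "This allows a more powerful and rigorous test of whether the intervention's effects are manifested quickly or over the long-term".

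Analysis c is secondary. The same section makes analysis a, a linear regression of the 36-month value on treatment and covariates, the primary efficacy analysis and the one that is powered. The 2018 SAP uses random-intercept models for baseline and 36 months only. It contains no three-visit model and does not expressly withdraw analysis c.

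**The concern.** With a random intercept and independent residuals, the changes from 0 to 18, 18 to 36 and 0 to 36 months all have the same variance. That is implausible for a process the protocol itself describes as gradual and long-term: if some patients accrue white-matter disease or lose gait speed faster than others, their paths fan out and the 36-month change varies more than the 18-month change. The fitted model averages the two variances.

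The harm runs in opposite directions. The 36-month difference looks more precise than it is, so it is declared too often. The contrast between early and late effects looks less precise than it is, so the test that the protocol presents as the stronger one loses sensitivity. Both bear on the time-course question and on the other mobility, cognitive and imaging outcomes for which analysis c is reused.

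**Working it through.** **Inputs.** The visits come from the protocol précis: outcomes "will be evaluated at baseline, and following 18 months and 36 months of therapy". The random-intercept form and the two treatment parameters come from analysis c. The timing contrast is `beta_E* - 2*beta_E`, the treatment difference in Y36 − 2·Y18 + Y0. Two inputs are not in the documents and are assumed: a two-sided 5% level, and q, the between-patient variance of slope per 18 months (t) divided by the residual variance (s). Slopes are taken as linear, and q is shown from 0.1 to 2.

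**The plan's own figure.** No power or precision is stated for analysis c. The stated 85% belongs to analysis a and reproduces: f² = 0.0533/(1 − 0.1800) = 0.065, noncentrality 140 × 0.065 = 9.1, F test on 1 and 135 degrees of freedom, power 85.0%. It does not bear on this point.

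**Variances, balanced data.** The random-intercept fit estimates the within-patient variance as s + t.

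| Quantity | True variance | Variance used by the fit |
|---|---|---|
| Y36 − Y0 | 2s + 4t | 2(s + t) |
| Y18 − Y0 | 2s + t | 2(s + t) |
| Y36 − 2·Y18 + Y0 | 6s | 6(s + t) |

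The ratios of reported to true standard error are therefore √[(1+q)/(1+2q)] at 36 months, √[2(1+q)/(2+q)] at 18 months and √(1+q) for the timing contrast. True size is the two-sided normal tail beyond 1.96 × ratio.

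| q | 36-month ratio | size | 18-month ratio | size | contrast ratio | size |
|---|---|---|---|---|---|---|
| 0.1 | 0.957 | 6.1% | 1.024 | 4.5% | 1.049 | 4.0% |
| 0.25 | 0.913 | 7.4% | 1.054 | 3.9% | 1.118 | 2.8% |
| 0.5 | 0.866 | 9.0% | 1.095 | 3.2% | 1.225 | 1.6% |
| 1 | 0.816 | 11.0% | 1.155 | 2.4% | 1.414 | 0.6% |
| 2 | 0.775 | 12.9% | 1.225 | 1.6% | 1.732 | 0.1% |

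At q = 1 the contrast is reported with twice its true variance (1.414² = 2).

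**Simulation check.** REML fits, 400 runs per setting, with 200 randomized and 30% dropout, gave the same directions: for q from 0.1 to 1 the 36-month ratio went from 0.95 to 0.75, and the contrast ratio from 1.09 to 1.36, not quite evenly.

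**What the optional clause would do.** Three readings, under the same linear-slope truth:

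- *Add a random linear slope, chosen by AIC.* Simulated size for q from 0.1 to 1 was 3.5–6.8% at 36 months and 4.0–7.0% for the contrast (Monte Carlo error about 1 point). AIC chose the slope in about 38–42% of runs at q = 0.1, about 91% at 0.25 and all runs at 0.5 and above.
- *Make the two visit shifts random and independent.* Large-sample fits, with intercept variance 1 or 3 times the residual variance, still leave the contrast ratio at 1.16 for q = 0.5 and 1.31 for q = 1, and 36-month size at 6.8–7.2% and 7.4–8.1%.
- *Make the two visit shifts random and correlated with the intercept.* That is 7 variance parameters (6 for the random effects, 1 residual) for a 3×3 covariance with 6. The split between residual and random effects is not identified, but the marginal covariance, and so the standard errors of the treatment effects, is that of an unstructured model.

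**The case against.** The strongest reply is that the displayed model is offered as an example and that patient-specific progression is expressly left open. That stands in part. Where slope variation is material, a sensible analyst using AIC to add a linear slope would nearly always do so, and the sizes in the table would not arise. But the protocol names neither AIC nor a linear slope. The coefficients it would make random are separate visit shifts, and one natural reading of that, independent shifts, leaves much of the error in the contrast. The safeguard may work; it is not promised.

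A reader might infer that the trial's main result carries an 11–13% false-positive risk. The documents do not support that. The powered analysis is the 36-month regression, which uses one visit and is untouched. In the SAP's two-visit models with complete data the variance of change is estimated directly, so the fault cannot arise. Analysis b also looks at 18 months separately, so the time course does not rest on analysis c alone.

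A reader might also infer from the 7-against-6 count that the clause cannot be used. It can: the count affects only how the variance is split, not the standard errors of interest.

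Finally, q is assumed. At q = 0.1 the 36-month size is only 6.1%. q may well be lower for gait than for MRI volume, but no document settles this.

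**Conclusion.** The concern holds for analysis c as displayed: with unequal rates of decline, the 36-month standard error is 0.96 to 0.77 of its true value and the timing-contrast standard error 1.05 to 1.73 times its true value, for q from 0.1 to 2. These figures rest on linear patient slopes, balanced data, a two-sided 5% level, and the optional clause not being used. If it is used to add a linear slope, the error largely disappears; independent visit effects remove only part of it. The defect is thus an unsuitable default covariance with an uncommitted remedy, in a secondary model that the plan presents as its more powerful test of timing and that the SAP does not replace.

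The figures do not extend to the binary and ordinal versions of analysis c. Nor do they extend to the Hypothesis 4 model, whose predictors are imaging values and which has no `beta_E` or `beta_E*`.

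**What to change.** For the continuous outcomes in analysis c, replace the random intercept and the clause about considering further random effects with an unstructured 3×3 within-patient covariance, fitted by REML with Kenward-Roger degrees of freedom. Test time course with the single contrast `beta_E* - 2*beta_E` from that model. For Hypothesis 4 the same covariance can be used, but the contrast does not apply. The binary and ordinal models need their own statement of random effects.

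The cost is a short text change and a line of code. The covariance has 6 parameters in place of 2, so four more are estimated, from up to 200 patients. With visit-specific means and complete data, the treatment estimates in analysis c do not change; with the roughly 30% attrition the protocol expects, they may shift slightly.

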7. STATISTICAL CONSIDERATIONS

7.1 General Design Issues

General considerations: Predictor, covariate, and dependent variables will be examined for outliers and data beyond the range of human performance. We will analyze variables on the original measurement scale, or on a scale that allows meaningful interpretation e.g., when an inverse transformation on a time measure results in a speed interpretation. The primary analyses (hypotheses 1, 2 and 3) will be intention-to-treat.

Hypothesis models, analysis plan, and power estimates for primary outcomes were developed with PASS 2008³⁵ and SAS PROC POWER³⁶ were used for estimation of power.

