Other mobility measures will also be examined as secondary outcomes in models otherwise identical to those in a, b, and c. The analyses will be repeated for cognition, with the speed obtained on Trailmaking B at T_{36} as the primary outcome and other cognitive measures as secondary outcomes. Additional secondary analyses will use logistic and ordinal models with the same predictors and incontinence presence and severity, respectively as outcomes; the progression model (c) will be fit as binary or ordinal generalized linear mixed models.

Hypothesis 4: Reduced total WMH and decreased markers of tissue damage on DTI at T_0 and at T_{36} are linked to better mobility at T_{36} . (Paths B+E)

The same outcomes will be used for this hypothesis as in hypothesis 1, with identical analyses except that WMH, and DTI indices (FA and MD) as continuous variables will be the primary predictor of interest. The power for this hypothesis as expressed as increased in explained variability (R^2) will be the same as for hypothesis 1: 85% power to achieve an increase in R^2 of 0.0533; we actually observed an increase in R^2 of 0.1658, to 0.2925, as the effect of tWMH, corresponding to a reduction in gait

velocity of 0.0063 m./sec. for each 0.1% increase in tWMH. The analyses will be repeated for gait velocity at T₁₈ with a model corresponding to analysis b, and for the following progression model replacing the model for analysis c:

$$Y_{i0} = b_{i0} + \beta_C (X_{i0}) + \text{cross sectional covariates} + \text{residual error}$$

$$Y_{i18} = b_{i0} + \beta_C (X_{i0}) + \beta_L (X_{i18} - X_{i0}) + \text{cross sectional covariates} + \text{longitudinal covariates} + \text{residual error}$$

$$Y_{i36} = b_{i0} + \beta_C (X_{i0}) + \beta_L (X_{i36} - X_{i0}) + \text{cross sectional covariates} + \text{longitudinal covariates} + \text{residual error}$$

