8.3 Sample Size and Randomization

We conservatively estimate that at least 140 of the original 200 participants will complete assessments at 35 months. We analyzed a subset of participants in our earlier observational study in order to mimic the results of the two treatment groups we expect to see in the intervention study. For a standard care arm, we selected participants in the observational study who had 24 hour systolic BP between 140 and 150 mmHg, inclusive, at follow-up, and for the intensive treatment arm, we selected participants with 24 hour Systolic BP between 120 and 130 mmHg, inclusive, at follow-up. A regression of gait velocity over 8 feet on our covariates age, sex, and 24 hour systolic BP at baseline showed an r^2 of 0.1267. If we see similar results in the intervention study, 140 participants (70 in each group) will give us 85% power to observe an increase in r^2 of 0.0533 to 0.1800. In our prior observational study, we saw an increase in r^2 of 0.1082 to 0.2349, with a difference in gait speed between the two simulated treatment groups of 0.15m./sec. While the 0.15m/sec gait speed difference between the low and high BP groups appears small, it represents only 2 years of observation. Mobility impairment linked to WMH is a long-term decremental process that limits gait velocity over 10 or more years. Thus a “small” 2-year differential is both believable and meaningful. We are therefore confident that the proposed study has ample power to find smaller yet clinically significant effects for our primary outcome. A regression of total WMH on covariates age, sex, and 24 hour systolic BP at baseline showed an r^2 of 0.1162. Similar results in the intervention study imply 85% power to observe an increase in r^2 of 0.0540 for the effect of the treatment arm, to 0.1702. We actually observed an increase of 0.0861, to 0.2023, in the prior observational study, corresponding to a difference between the two simulated treatment groups of 0.93% total WMH.

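### The hypothesis-4 progression model writes no visit effect, so its WMH-change slope can absorb an unrelated decline over time

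*Protocol*

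**What the plan says.** Analysis c in Protocol 8.2 has three equations, for baseline, month 18 and month 36. The two follow-up equations contain free-standing terms, β_L at month 18 and β_L* at month 36. These are the average changes in the reference group, listed separately from the longitudinal covariates. The parameters of interest there are the treatment-by-visit terms, described as "the difference in the outcome progression rate (mobility or imaging) between the treatment groups".

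For hypothesis 4 the protocol gives other equations, "and for the following progression model replacing the model for analysis c". Each follow-up equation contains a random intercept, β_C times baseline WMH, β_L times the change in WMH since baseline, and the same two unnamed covariate groups. No free-standing visit term appears. The slopes β_C and β_L are the parameters of interest, read as "the cross-sectional and longitudinal effects of the imaging measures on mobility over the 36-month follow-up". Time is mentioned for this model only once: "As secondary analyses we will consider interactions with treatment group and nonlinear effects in time". The model is to be repeated for other mobility and cognitive measures and, in binary and ordinal form, for incontinence.

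SAP item 6 also relates WMH change to outcome change, and it keeps a separate visit term beside WMH change. The SAP introduction says that it adds secondary analyses. It does not withdraw the protocol model.

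**The concern.** WMH change is zero for everyone at baseline and, on average, grows at each later visit. It therefore partly acts as a clock. If gait also slows over three years for reasons unrelated to WMH, a model without a visit effect can explain that slowing only through WMH change. The slope then mixes two things: whether people with more WMH accrual lose more speed, which is the question, and the fact that both averages move over time.

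Participants are 75 or older, so decline from other causes is plausible. The protocol's own earlier cohort points the same way: the gait contrast fell only "from a .15 m/sec. to a .1 m/sec. difference in gait velocity when WMH was added as a model predictor". That was a difference between blood-pressure groups, not a time trend, so it shows plausibility and nothing about size.

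At stake is a longitudinal WMH-function link that is reported where none exists, or overstated where one does, across every outcome for which the model is repeated.

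**Working it through.** **The plan's own figure.** Protocol 8.2 gives hypothesis 4 the same 85% power as hypothesis 1, for an R² increase of 0.0533. With covariate R² 0.1267, three covariates, N = 140 and an assumed two-sided 5% level, f² = 0.0533/(1 − 0.1800) = 0.0650 and the noncentrality is 140 × 0.0650 = 9.1. The noncentral F test gives 84.97%, so the figure reproduces. It belongs to the single-visit regression and is not in dispute.

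**Inputs from the documents.**
- N = 140 (Protocol 8.3) and three visits.
- WMH slope: a reduction in gait "velocity of 0.0063 m./sec. for each 0.1% increase in tWMH", that is 0.063 m/s per 1%.
- Gait SD: Protocol 8.3 reports an R² increase of 0.1082 "with a difference in gait speed between the two simulated treatment groups of 0.15m./sec". With equal groups and a group indicator uncorrelated with the covariates, SD = √((0.15²/4)/0.1082) = 0.228 m/s. A 40:60 split with R² 0.3 on the covariates gives √(0.15² × 0.24 × 0.7/0.1082) = 0.187.

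**Assumed inputs**, because the documents give no 36-month mean changes: WMH change with mean m and SD s; unrelated gait decline T over 36 months; linear trends; within-person correlation ρ = 0.5 to 0.7.

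**Formula.** In a random-intercept model without a visit effect, with WMH change growing linearly and independent of the other covariates, the spurious slope is

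T·m / (m² + k·s²), with k = 1 + 1.5(1 − ρ)/(1 + 2ρ),

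so k = 1.375 at ρ = 0.5 and 1.1875 at ρ = 0.7. It vanishes if T = 0 or m = 0. Its standard error is √[(1 − ρ)·SD² / (70(m² + k·s²))], where 70 = 140/2.

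**Example:** m = 0.3, s = 0.3, T = 0.05.
- ρ = 0.5: 0.015/0.21375 = 0.0702 per 1%, or 0.0070 m/s per 0.1%. The standard error is 0.0417, z = 1.68 and rejection 39%.
- ρ = 0.7: 0.015/0.196875 = 0.0762 per 1%, or 0.0076 per 0.1%. The standard error is 0.0336, z = 2.27 and rejection 62%.

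The spurious slope is thus larger than the 0.0063 that the protocol reports as observed.

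**Simulation** (1,000 trials per setting, REML random-intercept fits adjusted for baseline WMH and age, Wald test at 1.96) agrees with the formula. False-positive rates with a true WMH slope of zero, as written:

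| WMH change, mean (SD) | gait −0.025 m/s | gait −0.05 m/s |
|---|---|---|
| 0.1% (0.3%) | 7-8% | 10-16% |
| 0.3% (0.9%) | 6-9% | 10-17% |
| 0.3% (0.3%) | 14-19% | 39-63% |
| 0.5% (0.3%) | 19-27% | 53-78% |

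If either mean trend is zero, the rate is 4.8-6.3%. With visit terms it is 3.6-6.6% in all 30 null settings, and with a linear time term 3.5-6.5%. At gait SD 0.19 the 10-16% and 39-63% entries become 12-20% and 52-77%.

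**A true slope of 0.0063 plus an unrelated decline.** By the formula, the overstatement is the spurious slope divided by 0.063; the simulation agrees.
- WMH 0.3% (SD 0.9%), gait −0.05: about 20%.
- WMH 0.1% (SD 0.3%), gait −0.025: 30-35%.
- WMH 0.3% (SD 0.3%), gait −0.025: 54-60%.

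With visit terms the estimate is 0.0063-0.0064.

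**All decline through WMH.** Both versions are unbiased (0.0061-0.0065).

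**The case against.** The strongest reply is that the equations are schematic. Neither set prints a fixed intercept, so nobody would fit them literally. Time could sit in the undefined longitudinal covariates: if age were split into a baseline and a change part, as WMH is, the change part would be elapsed time. The mention of nonlinear time effects as an extension also suggests an unwritten linear term. On that reading a linear trend causes no problem.

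This does not settle the matter. In analysis c the two free visit terms already use up all shared time variation across three visits, so a time covariate beside them would be redundant. The same label is therefore unlikely to mean time there. No linear term is written anywhere for hypothesis 4.

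The second reply concerns size, and much of it stands. Every trend is assumed. The large rates need a WMH-change SD no larger than its mean or close to it. Applying the gait method to WMH gives a cross-sectional SD of √((0.93²/4)/0.0861) = 1.58%. With equal variances at both visits, a change SD of 0.3% then implies a 36-month correlation of about 0.98, and 0.9% implies about 0.84. The documents do not say which is nearer. At 0.9% the inflation is modest.

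Third, Protocol section 3 presents WMH accrual as the mechanism of decline. If that were the whole story, visit terms would only cost power. But that premise is what the analysis should test, so the model should not depend on it.

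Finally, SAP item 6 already provides an estimate with a visit term, though only for two visits.

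**Conclusion.** The concern holds. As written, the hypothesis-4 progression model omits a visit effect that both analysis c and SAP item 6 include, and its longitudinal slope is biased whenever mean WMH rises and gait has a decline of its own. The mechanism and direction are certain. The size is not: across the assumed trends, the false-positive rate runs from close to nominal (6-9%) to 53-78%, and in the settings examined a true slope is overstated by about 20% to 60%. There is no bias if either mean trend is absent or if all decline runs through WMH. The problem also goes, for a linear trend, if time was meant to be among the longitudinal covariates, but the plan does not say so.

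The scope is narrow: this secondary model and its repeats. Protocol 7.1 states "The primary analyses (hypotheses 1, 2 and 3) will be intention-to-treat", so hypothesis 4 is outside the primary set. The primary analyses, the 85% power figure, the single-visit month-18 and month-36 regressions, hypotheses 5 and 6, and the SAP models are untouched. The point should be fixed, but it does not threaten the trial's main result.

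**What to change.** Write fixed month-18 and month-36 effects into the hypothesis-4 progression equations and into their binary and ordinal versions. Give them a symbol other than the one used for the WMH-change slope. Define the longitudinal covariates and say whether time is among them. Base this model's longitudinal WMH conclusion on the version with visit effects; the version without them can be shown as a sensitivity analysis.

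This adds two parameters and needs no new data, but it costs precision. The standard error of the slope grows by the factor √(1 + m²/(k·s²)). In the simulations the increase is 3-5% when the WMH-change SD is three times its mean, 31-36% when the two are equal, and 75-84% at mean 0.5%, SD 0.3%. If all decline runs through WMH at the protocol's slope, power changes as follows:

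| WMH change, mean (SD) | as written | with visit effects |
|---|---|---|
| 0.1% (0.3%) | 22-32% | 20-29% |
| 0.3% (0.3%) | 35-49% | 23-28% |
| 0.5% (0.3%) | 49-74% | 21-29% |
| 0.3% (0.9%) | 94-98% | 91-98% |

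The power that is lost comes from treating the shared time trend as evidence about WMH, which is valid only if nothing else drives the decline.
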